# 9.7.2 Analysis of demography, disease details, prior and concomitant medication and other baseline data

Descriptive statistics will be used to summarize data on demographics, baseline characteristics, diagnosis, concomitant diseases, concomitant medication, and questionnaire scales and scores using mean ( $\pm$  SD), median, minimum, maximum for continuous variables, and category counts and frequencies (percentages) for categorical variables. Concomitant diseases on the case report form correspond to MedDRA terms. Concomitant medication will be coded using WHO's drug dictionary. Data will be recorded at each of the visits which will enable us to acknowledge and evaluate changes over time.

We will perform analyses for data obtained at each of the scheduled visits.

#### 9.7.3 Analysis of treatment data

Summary statistics will be provided for start of treatment, end of treatment, treatment duration, and reasons for treatment discontinuation.

#### 9.7.4 Analysis of primary outcome(s)

Our primary analysis will be after 12 and 24 months of observation; however, we will also perform analyses for the visits in between.

For the analyses of our primary outcome compliance we will use descriptive statistics to characterize compliance (in percent) by calculating mean ( $\pm$ SD), median, min, and max. This will include a stratified analysis according to the patients' pre-study experience with the BETACONNECTTM, i.e. new patients vs. experienced patients.

We will then investigate the association between baseline covariates and compliance in percentage using Analysis of Variance (ANOVA) and linear regression. First, we will use ANOVA to investigate mean differences in compliance for each of the categorical covariates. Second, we will use linear regression with compliance as the dependent variable and each of the covariates as independent variables. We will investigate univariate associations and then build a multivariable-adjusted model accounting for all covariates. With respect to the ANOVA analysis we will chose covariates as potential predictors that show a univariate association in the overall comparison using the F-test with a  $p \le 0.1$  and further investigate those in pairwise comparisons using both univariate and multivariable models. Finally, employing linear regression models, we will use a stepwise selection procedure to determine predictors of compliance, considering all covariates as potential predictors.

For the analyses of our co-primary endpoints we will likewise use descriptive statistics to characterize persistence and overall adherence (yes, no) using category counts and frequencies (percentages). This will include stratified analyses according to the patients' pre-study experience with the IMPACT number 18016; BETAPREDICT; Version 1.0, 12 February 2015 Page 42 of 75

BETACONNECTTM, i.e. new patients vs. experienced patients. In further analyses we will use logistic regression to investigate the association between baseline covariates as the independent variables and persistence and overall adherence as the dependent variables. The regression analyses will include investigating univariate associations, multivariable-adjusted associations, and finally as stepwise selection procedure to determine predictors of persistence and overall adherence, similar to the analysis of the endpoint compliance.

#### 9.7.5 Analysis of secondary outcome(s)

Descriptive statistics will be used to summarize data from questionnaire scales and scores as well as clinical data using mean ( $\pm$  SD), median, minimum, maximum for continuous variables, and category

counts and frequencies (percentages) for categorical variables. Concomitant diseases on the case report form correspond to MedDRA terms. Concomitant medication will be coded using WHO's drug dictionary. Data will be recorded at each of the visits which will enable us to acknowledge and evaluate changes over time.

We will perform analyses for data obtained at each of the scheduled visits.

We will use linear or logistic regression analysis (depending on the outcome scale) to evaluate the association between participation in the PTMS program and adherence to Betaferon® treatment as well as between participation in the PTMS program and depression, health related quality of life, self-management mechanisms, fatigue, and cognition at each visit as well as change of these variables over time.

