As part of the study we also plan to evaluate whether the **P**sycho-educative **T**raining for patients with **MS** (PTMS) may affect treatment adherence among patients using Betaferon®. The PTMS program is group-based trainings program that has been developed in 2009 and has been advanced since. It aims at helping patients deal with their MS as well as supporting them in developing a positive perspective of their lives, despite suffering from a chronic condition. The key focuses of the program are adequately coping with the disease, self-motivation for the required therapy, and continuity of treatment to ensure compliance/adherence.

The PTMS has been developed by a group of collaborating neurologists and psychologists. We have identified six neurology clinics, specialized in the treatment of MS offering the program as part of their clinical routine.

During clinical routine, the MS nurse or the treating neurologist recommends participation in the PTMS program if there is indication for inadequate coping, incompliance or deficit in knowledge about the disease. In general this pertains to all newly diagnosed patients, but also for example to experienced patients with "needle fatigue". Interested patients with the confirmed diagnosis of MS will be evaluated by a group leader. Exclusion criteria are severe depression or severe cognitive impairment. Groups consist of six to ten patients. The 90 minute sessions will be held with one to two weeks between each session until a series of 10 sessions has been completed. Sessions are mostly led by an experienced psychologist or MS nurse; however, sessions three, four and nine will be led by a physician or social worker. The program comprises knowledge transfer, exchange of experiences, role play, discussions, and self-reflection via diary.

The endpoints pertaining to the evaluation of the PTMS program, coping mechanisms, and social support will only be evaluated in patients from the six centers offering the program.

Approximately 90% of Betaferon® patients in Germany participate in the BETAPLUS® nurse support program. Hence, a subgroup analysis among those patients—while feasible—may not yield additional information and is not planned.

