# 9.3 Variables

The investigator collects historic data (demographic and clinical characteristics) from medical records if available, or else by interviewing the patient. Likewise, the investigator collects treatment related data during initial visit and follow-up visits. The investigator documents the study-relevant data for each patient in the electronic case report form (eCRF). All variables as indicated in **Table 1** are routinely collected during regular office visits. The CRF is available upon request (see Table 2: List of stand-alone documents, Annex 1).

Variables	Initial visit	Follow-up visit 1	Follow-up visit 2	Follow-up visit 3	Final visit
Demography	Х				
Employment status	Х	X	Х	X	Х
Education	Х				
Smoking	Х	X	Х	X	Х
Vitamin D intake	Х	Х	Х	X	Х
Other vitamin or nutrient intake	Х	Х	Х	X	Х
Medical history	Х				
Specific MS history	Х	X	Х	X	Х
Concomitant medication	Х	X	Х	X	Х
Concomitant diseases	Х	Х	Х	X	Х
Disease course		X	Х	X	Х
Expanded Disability Status Scale	Х	X	Х	X	X
Local skin reactions	Х	X	Х	Х	Х

Table 1: Tabulated overview on variables collected during the study

			-		
Expected/true treatment days	Х	X	X	Х	Х
Symbol Digit Modalities Test (SDMT)	Х		X		X
Participation in the BETAPLUS ® nurse support program	Х	X	X	Х	X
Participation in the PTMS program	Х	X	X	Х	X
Satisfaction with current way of Betaferon ® injection	Х	X	Х	Х	X
Injection site pain with current way of Betaferon ® injection	Х	X	X	Х	X
Flu-like symptoms following application of Betaferon ®	Х	X	Х	Х	X
Prophylactic analgesic use prior to Betaferon ® injection with current way of injection	Х	X	X	Х	X
Using electronic features of BETACONNECT TM	Х	X	X	Х	X
CES-D questionnaire (depression)	Х	Х	X	Х	Х
SF-36 questionnaire (HrQoL)	Х	X	X	Х	X
EQ-5D (utilities)	Х				Х
WEIMuS questionnaire (fatigue)	Х	Х	X	Х	Х
MSSM-R questionnaire (self- management)	Х	X	X	Х	X
CMSS questionnaire (coping)*	Х	X	X	Х	X
ISU-DYA Inventory (social support)*	Х	X	X	Х	X
Adverse Events		X	X	Х	Х
Medical Device related events and PTCs (including use errors)		X	X	Х	X
Reason for end of observation					Х

\*only for patients in centers, where the PTMS program is offered

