## 9.7 Data analysis

#### 9.7.1 Statistical considerations

Statistical analyses will be of explorative and descriptive nature. P-values <0.05 will be considered as statistically significant unless stated otherwise.

All variables will be analyzed descriptively with appropriate statistical methods: categorical variables by frequency tables (absolute and relative frequencies) and continuous variables by sample statistics (i.e. mean, standard deviation, minimum, median, quartiles and maximum). Continuous variables will be described by absolute value and as change from baseline per analysis time point, if applicable.

All analyses will be performed for the total study population (overall analysis) or when defined otherwise within a valid subpopulation. Patients receiving at least one dose of Betaferon® will be included in the analysis. Whenever reasonable, data will be stratified by subgroups (e.g. age, gender, baseline characteristics).

There will be no further documentation of patients fulfilling the following criteria (end of observation visit will be documented): 1. patients terminating Betaferon® treatment including those stopping treatment overall or switching to other treatments; 2. patients lost to follow-up; and 3. patients choosing to terminate study participation for any reason. During the final visit (in case of premature termination) the investigator should try to identify the date, when Betaferon® treatment was discontinued. If this date cannot be identified or approximated, e.g. if a patient is lost to follow-up, the date of the last documented visit should be chosen. Further, the investigator should make every effort to identify the reason, why a patient decides to terminate the study. Reasons for study termination will be displayed using descriptive statistics.

All therapies documented will be coded using the World Health Organization – Drug Dictionary (WHO-DD). Medical history, any diseases and AEs will be coded using the latest Medical Dictionary for Regulatory Activities (MedDRA) version.

All statistical details including calculated variables and proposed format and content of tables will be detailed in the Statistical Analysis Plan (SAP). The SAP will be finalized before study database lock. The SAP is available upon request (see BF1502\_SAP\_final\_yyyymmdd Table 2: List of stand-alone documents, Annex 1).

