## 9.7.7 Bias, confounding and effect-modifying factors

In general data collected in this study may suffer from biases (e.g. interviewer bias, either by systematic differences in data recording or different interpretation of information on exposure or outcome for different patients, reporting as well as selection bias). Information bias with respect to

injection data will be avoided since the autoinjector automatically records injection related data; however information obtained from patients may suffer from recall bias, which is inherent to the study design. Further, prospective studies are prone to bias from loss to follow-up or change in methods over time. To decrease reporting bias source data verification will be performed in at least 10% of the sites. Sites will be selected according to several criteria, main criteria for site selection will be: availability of suitable patients and an equal geographical distribution. Patients should be enrolled consecutively. Investigators should select patients to be documented in the study only based on eligibility according to inclusion and exclusion criteria. No further selection should be applied. However, sites agreeing to participate in the study may not be equally distributed across Germany; hence, patients enrolled may not be representative of all German MS patients.

Primary and secondary outcome variables will be analyzed with regard to different baseline factors. However, unknown and unmeasured risk factors for the outcome variables will exist and might lead to confounding when comparing results in different subgroups and when comparing study results with historical results from clinical studies.

For the secondary objectives we will also evaluate post-baseline variables with respect to adherence. Potential bias may arise from reciprocal influence of these variables on each other during the study course, requiring extreme caution when interpreting these results.

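### The PTMS regressions in Section 9.7.5 name no baseline-score covariate and no leading analysis, so a baseline difference between non-randomised groups carries into the visit-score contrast

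*Protocol*

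**What the plan says.** Section 9.7.5 uses linear or logistic regression, according to the outcome scale, for the association "between participation in the PTMS program and depression, health related quality of life, self-management mechanisms, fatigue, and cognition at each visit". The same sentence plans this for the change in each measure too. The exposure, the model class and two outcome forms (score at the visit, and change) are therefore fixed. No covariate is listed or excluded, and neither form is said to lead.

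Section 9.7.4 does separate univariate from multivariable models and lists covariates, but for compliance, persistence and overall adherence only.

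Section 9.7.7 adds a general statement: "Primary and secondary outcome variables will be analyzed with regard to different baseline factors". It does not mention the PTMS models or the initial-visit score of the same scale.

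All five measures exist at the initial visit. In the variables table of Section 9.3, the row that begins "CES-D questionnaire (depression" is marked for every visit, as are SF-36, WEIMuS and MSSM-R. SDMT is marked for the initial visit, follow-up visit 2 and the final visit.

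On entry to PTMS, Section 7 says: "Exclusion criteria are severe depression or severe cognitive impairment". It also says that the programme is recommended where coping, compliance or knowledge of the disease is poor. Section 8.2 describes the comparison as one between patients of PTMS and non-PTMS centres, while Section 9.7.5 speaks of participation.

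**The concern.** The PTMS comparison is observational, and the entry rules bear on the outcomes being compared. The exclusions concern depression (CES-D) and cognition (SDMT). The recommendation rule concerns matters that MSSM-R measures in its adherence and knowledge subscales. Participants may therefore start better on some scales and worse on others.

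A later-visit score that is not adjusted for its starting value carries part or all of that initial difference into what is reported as an association with the programme. The change score handles the same difference in another way, and can point in the opposite direction. Because the plan does not say which form leads, a reader who sees the two disagree has no rule for choosing between them.

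**Working it through.** **The plan's own figure.** The only PTMS power statement (Section 9.5) concerns compliance: a 7-point difference, SD 8 or 10, alpha 0.05, power above 90%. For a two-sample t-test the noncentrality is (7/SD) x sqrt(n1 n2/(n1+n2)). For 30 vs 100 at SD 10 this is 0.7 x sqrt(3000/130) = 3.36, which gives 91.6% two-sided. The other group sizes at SD 10 give 94.8% (30/220), 99.7% (60/190) and 99.96% (90/160). At SD 8 all are 98.7% or more. The statement reproduces. The protocol gives no SD, effect size, correlation or power for the five scales, so what follows rests on assumptions.

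**Bias when the programme has no effect.** Assume equal SDs at both visits, initial-to-later correlation rho, and an initial difference D in SD units. Let V be the expected difference in the later score.

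- Visit-score contrast: V
- Change contrast: V - D
- Baseline-adjusted contrast: V - rho x D

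If patients are selected on the baseline score, the difference regresses to the mean and V = rho x D. If the centre groups differ stably, V = D. With D = 0.3:

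| Situation | rho | Visit score | Change | Baseline-adjusted |
|---|---|---|---|---|
| Selection on baseline | 0.5 | +0.15 | -0.15 | 0 |
| Selection on baseline | 0.7 | +0.21 | -0.09 | 0 |
| Stable centre difference | 0.5 | +0.30 | 0 | +0.15 |
| Stable centre difference | 0.7 | +0.30 | 0 | +0.09 |

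Simulation agreed with these values to within 0.005 SD.

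To give D a scale, suppose that the top 10% of depression scores are kept out of PTMS and 25% of the rest take part. Neither percentage is in the protocol. Then D is about -0.25 SD. At rho 0.5 the visit contrast is 0.5 x (-0.25), about -0.13 SD. The change contrast is -0.5 x (-0.25), about +0.13 SD. The adjusted contrast is 0.

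**Power.** The residual variance relative to the visit score is 1 (visit), 2(1 - rho) (change) and 1 - rho squared (adjusted). Set the effect so that the unadjusted visit score has 80% power at two-sided alpha 0.05, with no baseline imbalance. The results are the same to the figures shown at all four group sizes in Section 9.5:

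| rho | Visit | Change | Adjusted |
|---|---|---|---|
| 0.3 | 80% | 66% | 84% |
| 0.5 | 80% | 80% | 90% |
| 0.7 | 80% | 95% | 97.5% |

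The gain shrinks when power is already high. At 0.7 SD, which is the compliance effect and not one stated for these scales, and rho 0.5, power rises from 91.6% to 97.1% (30/100), from 94.8% to 98.5% (30/220) and from 99.7% to about 100% (60/190). At 90/160 it is about 100% either way.

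**The case against.** The strongest reply is that the protocol is silent on covariates and has not decided against them. It says "All statistical details including calculated variables and proposed format and content of tables will be detailed in the Statistical Analysis Plan (SAP". That plan is not at hand, and covariate lists for secondary models are often placed there. This stands against one reading: a reader might infer that the sponsor chose to leave the baseline score out, and the text does not support that. What remains is that the protocol itself fixes two forms that can disagree and ranks neither.

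A second reply is that adjustment is not a sure remedy. With a stable difference between centre groups, which the wording of Section 8.2 makes possible, change is the unbiased form and the adjusted contrast is off by (1 - rho) x D. This also stands. It rules out the inference that the planned analyses always give two biased answers of opposite sign, and it argues against dropping the change analysis. It does not rescue the unadjusted visit score, which is further from zero than the adjusted one in both situations.

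A third reply is that "Statistical analyses will be of explorative and descriptive nature", and that reporting both forms would expose any disagreement. The first half limits the importance of the point. The second half is only partly an answer, since exposing a disagreement does not tell the reader how to read it, and "P-values <0.05 will be considered as statistically significant unless stated otherwise" still applies to both results.

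**Conclusion.** The concern holds as a minor point. For post-baseline visits, the unadjusted visit-score contrast carries forward rho x D under selection on the baseline score, or the full D under a stable centre difference. Adding the same scale's initial-visit score reduces this to 0 or to (1 - rho) x D respectively, and its residual variance is no larger than that of either planned form. Visit and change contrasts of opposite sign with no effect arise in the first situation only.

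A reader might also take from the power table a fixed loss of about 10 points. That figure belongs to one cell, rho 0.5 with 80% unadjusted power. Over rho 0.3 to 0.7 the gain on the visit score is 4 to 17.5 points, and at 0.7 SD with rho 0.5 it is 0 to 5.5 points. The size of D, its direction on each scale and rho are all unknown from the protocol. No primary conclusion depends on these analyses.

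**What to change.** In Section 9.7.5, or in the SAP with a reference from it:

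- For each post-baseline visit, regress the score on PTMS group with the patient's initial-visit score on the same scale as covariate, and name this as the leading analysis. For cognition this means follow-up visit 2 and the final visit.
- Keep the change-score regression as a declared sensitivity analysis, and say that it is the unbiased form if the centre difference is stable.
- Keep the initial-visit comparison as descriptive.
- Show patients with PTMS before or at the initial visit separately, since their baseline score already follows exposure. Section 9.2.7 lists a yes/no item on participation at that visit. Confirm that it also identifies courses completed earlier.

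The cost is a few sentences. The five scales are already collected at the initial visit. The drawback is that patients without a baseline score, or with earlier PTMS, do not contribute to the adjusted estimate. The protocol does not give their number, so it should be reported.

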#### 8.2 Secondary objective(s)

Secondary objectives are to evaluate at each visit:

- Satisfaction with the BETACONNECTTM autoinjector,
- Injection site pain,
- Flu-like symptoms following Betaferon® application,
- Analgesic use prior to Betaferon® application,
- Intake of vitamin D, other vitamins, and nutrients,
- If adherence to Betaferon® treatment is associated with:
  - depression,
  - health related quality of life,
  - coping mechanisms\*,
  - self-management mechanisms,
  - social support\*,

- fatigue, and
- cognition.
- If adherence to Betaferon® treatment at 12 (24) months is associated with number of relapses at 12 (24) months.
- If adherence to Betaferon® treatment at 12 (24) months is associated with EDSS change at 12 (24) months.
- If adherence to Betaferon® treatment is associated with utilities of treatment (only baseline and final visit).
- With respect to the subgroup of patients participating in the PTMS program (participants from PTMS centers vs. participants from non-PTMS centers):
  - At each visit, if the PTMS program is associated with:
    - treatment adherence,
    - depression,
    - quality of life,
    - self-management mechanisms,
    - fatigue,
    - cognition.
- In the subgroup of patients participating in the PTMS program:
  - At each visit evaluation of:
    - social support,
    - coping behavior.

\*only for patients participating in the PTMS program.

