# Enrollment / Initial visit

Once a patient is found eligible for inclusion, the investigator will inform the patient about the study. Where applicable, this will include discussing the consent form and asking the patient to read and - when agreeing to participate - sign the informed consent.

Typical information to be collected at the baseline visit includes:

- Date of visit
- Date of birth (at least year)
- Sex (female, male)
- Race / ethnicity (Caucasian, asian, black, other)
- Height (cm)
- Weight (kg)
- Smoking (current, past, never)
- Employment status (employed, retired, keeping house, student, seeking work, self-employed, other, not reported)
- Education level (elementary education, secondary education, college or university education, not reported)
- Marital status (married/partnership, single)
- Medical history
  - Concomitant diseases
  - Concomitant medication
    - Trade name or INN
    - Start date (at least year)
    - Stop date or "continued"
    - Daily dose, if applicable
    - Indication
- Intake of vitamin D supplements (yes vs. no; if yes which dosage?)
- Intake of other nutrients or vitamins (yes vs. no)

IMPACT number 18016; BETAPREDICT; Version 1.0, 12 February 2015

- Specific MS history
  - Date of first clinical event suggestive of MS (DD/MM/YYYY)
  - Date of initial diagnosis (DD/MM/YYY)
  - diagnostic criteria
    - o according to McDonald criteria
    - o according to Poser criteria (CDMS)
  - Number of further demyelinating events/relapses (number during past 2 years)
    - If number >0: date of onset (DD/MM/YYYY), ongoing
  - Concomitant diseases of special interest
    - Depression
    - o Anxiety
    - o Fatigue
  - Betaferon® administration record
    - Betaferon® treatment (ongoing/naive)
    - Date of first Betaferon® injection (DD/MM/YYYY)
  - Current application form for Betaferon® (prior to study)
    - Manual injection (yes/no)
    - Use of auto-injection device (yes/no)
      - If Yes, please tick (BETACONNECTTM, BETACOMFORT®, BETAJECT Comfort®, BETAJECT lite®, other)
  - Treatment days with Betaferon® during last month
    - Number of expected treatment days
    - Number of true treatment days
    - o N/A
  - Participation in the BETAPLUS® nurse support program (yes/no)
  - Participation in the PTMS program (yes/no)

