#### **Follow-up visits during treatment**

Typical information to be collected at follow-up visits include:

- Date of follow-up visit (DD/MM/YYYY)
- Study continued (yes/no), if no
  - please complete end of observation visit

IMPACT number 18016; BETAPREDICT; Version 1.0, 12 February 2015

- Smoking (current, past, never)
- Employment status (employed, retired, keeping house, student, seeking work, self-employed, other, not reported)
- Marital status (married/partnership, single)
- Concomitant diseases
- Concomitant medication
  - Trade name or INN
  - Start date (at least year)
  - Stop date or "continued"
  - Daily dose, if applicable
  - Indication
- Disease course
  - Number of further demyelinating events/relapses (enter 0 if no further event since last visit)
    - If number >0: date of onset (DD/MM/YYYY)/ongoing
- Specific MS history
  - BETACONNECTTM auto-injector device still used (yes/no)
    - If no, please tick: Betaferon® treatment (ongoing/prematurely discontinued/unknown)
    - If ongoing, please specify which way of injection is used
      - Manual injection, BETACOMFORT®, BETAJECT Comfort®, BETAJECT lite®, other
    - If prematurely discontinued
      - last date of Betaferon® injection (DD/MM/YYYY)
      - reason [adverse event (please complete AE page), lack of efficacy, pregnancy, patient's wish, choice of other treatment (please specify)]
- Treatment days with Betaferon® since last visit
  - Number of expected treatment days
  - Number of true treatment days
- Local skin reactions (yes/no)
  - If yes; please tick

- a) (redness, other discoloration, hematoma, induration, lipodystrophy/atrophy, necrosis)
- b) (mild, moderate, severe)
- Participation in the BETAPLUS® nurse support program (yes/no; if no, please specify termination date)
- Participation in the PTMS program (yes/no; if no, please specify termination date)
- Intake of vitamin D supplements (yes vs. no; if yes which dosage?)
- Intake of other nutrients or vitamins (yes vs. no)
- EDSS
- Patient QQ results available (yes/no), if yes
  - please send back
- SF-36 results available (yes/no), if yes
  - please send back
- CES-D results available (yes/no), if yes
  - please send back
- WEIMuS results available (yes/no), if yes
  - please send back
- SDMT results available (yes/no) [only follow-up visit 2], if yes
  - please send back
- CMSS results available (yes/no)\*, if yes

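### The PTMS change-over-time analysis does not separate patients who attended the programme before enrolment, and the listed visit data allow this only in part

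*Protocol*

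**What the plan says.** Protocol section 9.7.5 plans linear or logistic regressions of adherence and the patient-reported and cognitive outcomes on participation in PTMS. They cover depression, quality of life, self-management, "fatigue, and cognition at each visit as well as change of these variables over time". Participation enters as one variable, with no split by when the course was attended.

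Section 8.2 introduces the same objective as concerning patients in the programme, but sets the comparison as "participants from PTMS centers vs. participants from non-PTMS centers". The PTMS power statement in section 9.5 is also by centre.

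Section 7 describes PTMS as a "group-based trainings program that has been developed in 2009 and has been advanced since", run by six clinics "specialized in the treatment of MS offering the program as part of their clinical routine". On who is referred, it says: "In general this pertains to all newly diagnosed patients, but also for example to experienced patients". The course has 10 sessions, one to two weeks apart.

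Section 9.2.2 admits patients already on Betaferon as well as those about to start, and section 9.2.3 has no exclusion for earlier PTMS attendance. The initial-visit list in section 9.2.7 has "Participation in the PTMS program (yes/no" and nothing more on timing. The follow-up and final visits have "Participation in the PTMS program (yes/no; if no, please specify termination date". No visit lists a start date. Section 9.7.4 includes PTMS participation among the candidate baseline predictors, so some patients are expected to be participants by enrolment.

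**The concern.** A change-from-baseline analysis of a programme is informative only where baseline comes before the programme. For a patient who finished PTMS before the initial visit, the first depression, quality-of-life, self-management, fatigue and cognition scores are already post-programme values, and later change cannot show a benefit that has already occurred. A patient part-way through the course at enrolment is an intermediate case.

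If such patients are mixed with those who start after baseline, a null change result has two explanations that cannot be told apart: PTMS does nothing, or it had already worked. Section 9.7.7 recognises the same kind of problem for the autoinjector, separating naïve from experienced patients, and extends the reasoning to experience with the drug. It does not do so for PTMS.

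**Working it through.** **1. Can the course precede baseline?** Ten sessions have nine gaps of one to two weeks, so the course lasts 9 × 1 = 9 to 9 × 2 = 18 weeks. The programme was about six years old at the protocol date (2009 to 2015), and patients on established treatment are eligible. Completion before enrolment is therefore possible. The protocol does not say how common it is.

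**2. Where does an earlier attender fall?**

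| Definition of exposed | Earlier attender is in | Effect on change contrast | Effect on comparison at each visit |
|---|---|---|---|
| Patient of a PTMS centre (8.2, 9.5) | exposed group, with current and never attenders of that centre | diluted | not diluted by the timing |
| Ever attended | exposed group | diluted | not diluted by the timing |
| Attending now | comparator | not diluted if the benefit is complete and lasts | comparator contaminated |

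Section 9.7.5 does not say which definition applies. Pooling follows directly from the centre contrast. Under a participation-based analysis it is an inference.

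**3. Can the listed data separate the groups?** In part. A baseline no followed by a yes, or by a termination date after enrolment, points to an in-study attender. A termination date before the initial visit identifies an earlier one. A baseline yes remains ambiguous: it may mean a finished course, the first session or the tenth.

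**4. The plan's own figure.** Inputs from section 9.5: difference 7 points, SD 8 or 10, alpha 0.05 (two-sided assumed), group sizes 30/100, 30/220, 60/190 and 90/160. Power comes from the noncentral t with noncentrality δ / [SD × √(1/n₁ + 1/n₂)]. The least favourable case is 30/100 with SD 10: 7 / (10 × 0.208) = 3.36, power 91.6%. All eight combinations exceed 90%, so the statement reproduces. It concerns a between-group difference in compliance, not change from baseline.

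**5. Illustration of dilution.** Let p be the share of the exposed group who attended before baseline, and r the fraction of the effect that still accrues to them afterwards. The expected contrast in change is δ × [1 − p(1 − r)]. The protocol gives neither p nor r, and no effect size or SD for any change score. The 7 points and SD 10 from section 9.5 serve only as a stand-in, with r = 0:

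| p | Contrast | 30/100 | 30/220 | 60/190 | 90/160 |
|---|---|---|---|---|---|
| 0 | 7.0 | 92% | 95% | 99.7% | >99.9% |
| 10% | 6.3 | 85% | 90% | 99% | 99.7% |
| 25% | 5.25 | 71% | 77% | 94% | 98% |
| 50% | 3.5 | 39% | 43% | 65% | 75% |
| 75% | 1.75 | 13% | 15% | 22% | 26% |

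A simulation that allows for the extra variance of a mixed group gives 75% (30/220) and 97% (90/160) at p = 25%, and 43% and 73% at p = 50%. Under the centre contrast, never-attenders at PTMS centres would dilute the result further. Their share is not given either.

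**6. Does restriction to new attenders recover power?** Assume an effect of 0.5 SD, 60/190 and p = 50%.
- r = 0: the pooled effect is 0.5 × 0.5 = 0.25 SD, power 39%. New attenders only (30/190, 0.5 SD) give 72%.
- r = 0.5: the pooled effect is 0.5 × (1 − 0.5 × 0.5) = 0.375 SD, power 71%, against the same 72%.

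Restriction gains much in the first case and almost nothing in the second. With more residual effect it loses power.

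**The case against.** The strongest reply is that the protocol never says earlier and in-study attenders are pooled. Section 9.7.1 leaves calculated variables to the SAP, which could define participation and use the follow-up termination dates. Section 9.2.7 lists only typical information, and the case report form is a separate document. This stands in part: under a participation-based analysis the pooling is inferred, and some separation is possible. It does not dispose of the point. The centre contrast in 8.2 and 9.5 does pool, and a SAP cannot reliably reconstruct timing that was not collected at baseline.

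The reply on scope stands in full. Dilution concerns change over time only. Comparisons at each visit and compliance over the observation period are not diluted in this way. The objective is secondary and exploratory, and section 9.7.7 already urges caution with associations involving post-baseline variables.

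A reader might infer three stronger points that the documents do not support:
- Survivor selection flatters the persistence of earlier attenders. Every patient already on Betaferon at enrolment is a survivor, attender or not. If PTMS helps persistence, the non-attenders would be the more strongly selected, so the direction is not established.
- Adjusting for baseline would remove the PTMS effect. Section 9.7.5 plans no such adjustment.
- Restricting to new attenders always more than repays the smaller group. Step 6 of the working shows that it need not.

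**Conclusion.** The point holds in a limited form. The protocol admits patients who may have attended PTMS before enrolment, lists no item that reliably identifies them, and analyses change over time without separating them. Counted as exposed, they pull the change contrast towards zero to the extent that their benefit arose before baseline. Counted as non-participants, they contaminate the comparator at each visit.

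The size cannot be determined. The figures rest on an assumed share p, an effect borrowed from compliance, and a benefit that arises during the course and lasts. At p = 50% with no further change the contrast halves, and power in the stand-in falls to 39–75%; at p = 25% it is 71–98%. If the benefit wanes, earlier attenders could worsen after baseline and the distortion would be larger. If much of it accrues after baseline, the distortion is smaller. The primary objective and the stated power above 90% are untouched. This is a cheap improvement to a secondary analysis.

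**What to change.** - On the initial-visit page, record PTMS as never, ended before enrolment or attending now, with start and end dates.
- Reconcile the centre-based contrast in sections 8.2 and 9.5 with the participation-based regression in 9.7.5, and state how an earlier attender is classified.
- In 9.7.5, present change over time separately for patients not yet exposed to PTMS at baseline and for those who attended before enrolment. Patients already under way at the initial visit can be identified from the start date. Keep the pooled analysis as supportive.

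The cost is a few form fields, amended wording in these sections, and a smaller PTMS group in the stratified change contrast. That contrast may be less precise than the pooled one, which is a reason to show both.
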